5.1. Specimen Handling and Transportation

Peripheral or arterial blood samples (10 mL) will be obtained at four time points for a total of up to 40 mL of blood. The four time points are: before study drug is administered (By 6 hours of ICU admission), 0-24 hours after administration of first dose of study drug, 48-72 hours after administration of first dose of study drug, and again 96-120 hours after administration of first dose of study drug . Missing time points does not disqualify patient for study participation and is not a protocol deviation. Sub-populations of

white blood cells will be measured using flow cytometry and mononuclear cells will be isolated using Ficoll-Paque[™]. Blood will not be collected if patient develops a hemoglobin less than 7 g/dL or requires a transfusion. COVID-19 considerations are outlined in Appendix 16.7. Blood specimens will be transported to xxxx for analysis. Samples from non-xxxx hospitals may be stored and transported under various conditions not listed above but that are acceptable.

5.2. Effect of Ceftriaxone on CD73

CD3+ lymphocytes obtained from peripheral blood before administration of study drug will be adjusted to a concentration of 106 cell/mL and incubated with 50 mcg/mL ceftriaxone or vehicle for 24 hours. Expression of CD73 in subpopulations of CD3+ T cells will be determined using multi-parametric flow cytometry after staining cells with antibodies: CD3FITC-CD73PE-CD4PeCy7-CD8APC-CD39APC/Cy7-DAPI. CD73 levels in both CD4+ and CD8+ subpopulations of CD3+ T cells will be measured.

5.3. T cell-mediated Adenosine Production

CD3+, CD4+CD3+ or CD8+CD3+ T cells will be incubated with 20 μ M [8-14C] ADP (American Radiolabeled Chemicals). Radioactive [8-14C] adenosine generated by T cells will be separated from [8-14C] nucleotides on columns of acidic aluminum oxide (1.3 g/column) by elution with 4 ml 0.005 N hydrochloric acid. T lymphocyte generation of adenosine will be assayed.⁶⁰

5.4. CD73/ Adenosine-mediated T Cell Activation

Analysis of genes involved in T cell response will be performed with total RNA isolated from CD3+ lymphocytes after their incubation in the presence of vehicle, ceftriaxone, or in combination with AMP. Total RNA will be isolated using RNeasy Mini Kit (Qiagen) and cDNA will be generated using RT² Nano PreAMP cDNA Synthesis Kit (SABiosciences). Gene expression will be analyzed using Oligo GEArray[®] Human T-cell and B-cell Activation Microarray (SABiosciences, OHS-053). This panel of 113 genes includes CD28, CD3E, IL10, IL12B, IL18, IL27, NCK1, and NCK2 genes involved in regulation of T cell proliferation and regulators of Th1 and Th2 development such as IFNG, IL10, IL12A, IL13, IL4, IL5, ITGAX, TLR2, TLR4, TLR7, and 11TLR9.

5.5. CD73 and Pro-inflammatory Cytokines

Multi-parametric flow cytometric analysis will be conducted on whole blood cells before study drug and on study-day 1 and study-day 3. Cells will be stained with CD4FITC-CD73PeCy7-CD8PerCP-CD3APC/Cy7 following fixation, permeabilized (BD Cytofix/CytopermTM) for intracellular staining with anti-IFN- γ (Clone 25723) or anti-TNF- α (Clone 6402) antibodies (R&D System/Bio-techne). The percentage of CD3+ T cells, CD4+ and CD8+ subpopulations, and CD73 expression on T lymphocytes will be determined within DAPI negative (viable) cell populations using MACSQuant. Myeloid cells will be analyzed to validate ceftriaxone's effect in lymphocytes. Neutrophils and monocytes will be gated and cell surface expression of CD73 and production of TNF- α assayed as described for lymphocytes.

6. Data Collection

Data will be collected to screen, recruit, and determine eligibility of prospective OHCA subjects. Prior to consent, certain information will be gathered for screening including name, date of birth, MRN, date/time of ICU admission, details surround the cardiac arrest, pre-existing terminal disease, medical

history, infection status, allergies, legal guardianship/prisoner, and medical status. Screening logs will be maintained and reasons for exclusion will be recorded. Data collection in REDCap will be completed for patients who are screened and/or enrolled in the PROTECT Study. REDCap is a secure, web-based application for data capture.⁶¹ Data collected may follow the International Liaison Committee on Resuscitation's Utstein criteria for OHCA.⁶² Data will be collected by research coordinators or study investigators from medical records, family members, ambulance run reports, or other sources. The REDCap data collection tool has been modified to ensure demographic data for EFIC patients is captured at XXXX. In addition to the data outline below, information on serious adverse events, study drug and trial completion will be collected.

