2.6. Anti-inflammatory Effects of Ceftriaxone

Ceftriaxone reduced IFN- γ and TNF- α in the injured parietal cortex and improved learning and spatial memory function in a rat model of traumatic brain injury.²⁶ Ceftriaxone also reduced IFN- γ and IL-17 secretion in a mouse model of multiple sclerosis by altering antigen presentation and activation of myelin-specific T lymphocytes.²⁷ Other studies have shown ceftriaxone dampens excitotoxicity in by decreasing glutamate transporter function.^{26,28-31} Because excitotoxicity is a possible cause of secondary brain injury following OHCA, ceftriaxone's ability to attenuate this response is promising.³²

T cells promote neuroinflammation and neuronal cell death via IFN- γ and TNF- α .³²⁻³⁴ Our preliminary data showed incubation of CD3+ T-cells from human peripheral blood with ceftriaxone for 24 hours increased expression of CD73. CD73 is an adenosine-generating enzyme, and adenosine has potent immunosuppressive and anti-inflammatory effects in T cells. Consistent with this concept, the PROTECT study will determine if CD73 level is inversely correlated with IFN- γ levels in both CD4+ and CD8+ T cells.

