3.1.1. Centrifugation of specimens to separate cells and fluid part of the blood or endotracheal sputum will be performed under the hood in PowerSpin LX clinical centrifuge (UNICO) placed inside the BSL2 hood.

3.1.2. After centrifugation, the fluid part of the blood or endotracheal sputum will be transferred into 1.5 eppendorf screw-capped tubes, containing information on specimens. These tubes will be placed inside the eppendorf storage boxes containing biohazards signs and information on specimens, sprayed

with 70% ethyl alcohol, and stored at -80 in a designated rack, containing biohazards signs, until further analysis.

3.1.3. Cells in the pellet will be carefully transferred into 1.5 ml eppendorf tubes with secure screw caps and washed with cold FACS buffer containing 2 mM EDTA and used for the staining of cell surface antigens and flow cytometric analysis.

3.1.4. The original specimens containers, BD vacutainer, and Lukens containers trap will be sprayed with 70% ethyl alcohol and placed in smaller biohazard bags and secured with adhesive autoclave tape. This bag will be placed into biohazards waste, located close to the BSL2 hood.

3.2. Flow cytometric analysis.

3.2.1. Cells in 1.5 ml eppendorf tubes will be stained using an array of antibodies. Unbound antibodies will be removed through centrifugation (inside the hood) and supernatant aspiration using a vacuum trap system with 1% sodium hypochlorite solution. During the entire procedure cells will be washed for five (5) times with FACS buffer containing 2 mM EDTA to remove any non-specifically bind proteins. Washout buffer will be removed using a vacuum trap system with 1% sodium hypochlorite solution.

3.2.2. Flow cytometry samples will be transferred to Flow cytometry Core using a transport container with a biohazard sign and information on samples. Cells will be analyzed using flow cytometer MACSQuant 10 located in the core facility. To prevent aerosol formation during flow cytometry, the automatic regimen of sample mixing will be disabled. Laminar fluidic system performance will be monitored using Fluorochrome vs. Time plots.

3.2.3. All flow cytometry samples will be wasted immediately after analysis into the waste system, containing 1% sodium hypochlorite solution and securely connected to the fluidic system. No flow cytometry samples will be reused for any other analysis. No flow cytometry samples will be saved after the analysis.

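### Section 5.5 places a DAPI-exclusion viability gate in a workflow that permeabilises the cells; on its most natural reading, the gate behind CD73 and the T-cell subsets does not select viable cells

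*Combined protocol and SAP*

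**What the plan says.** Section 5.5 sets out a flow-cytometry analysis at three times: "Multi-parametric flow cytometric analysis will be conducted on whole blood cells before study drug and on study-day 1 and study-day 3". The preparation is given in one sentence: "Cells will be stained with CD4FITC-CD73PeCy7-CD8PerCP-CD3APC/Cy7 following fixation, permeabilized (BD Cytofix/CytopermTM) for intracellular staining", with antibodies against IFN-γ or TNF-α. The following sentence gives the readouts: the share of CD3+ T cells, the CD4+ and CD8+ subsets, and "CD73 expression on T lymphocytes will be determined within DAPI negative (viable) cell populations using MACSQuant".

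The section then extends the procedure to myeloid cells: "Neutrophils and monocytes will be gated and cell surface expression of CD73" and TNF-α production are to be assayed in the same way as for lymphocytes.

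Two other places describe related staining:

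- Section 5.2, the in-vitro experiment on cells taken before study drug, uses the panel "CD3FITC-CD73PE-CD4PeCy7-CD8APC-CD39APC/Cy7-DAPI". It includes DAPI and describes no fixation.
- Appendix 16.7 (COVID-19 handling) says that washed cells are "used for the staining of cell surface antigens and flow cytometric analysis", again with no fixation or permeabilisation step.

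The purpose of measuring CD73 and a cytokine together is in section 2.6: "the PROTECT study will determine if CD73 level is inversely correlated with" IFN-γ in CD4+ and CD8+ T cells.

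**The concern.** A dye-exclusion gate works because a live cell's membrane keeps the dye away from its DNA. Permeabilisation opens that membrane on purpose, so that cytokine antibodies can get in. If DAPI is read after that step, it can reach the nucleus of cells that were alive at collection as well as those that were dead. The DAPI-negative region then no longer means viable; it is either close to empty or set arbitrarily.

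At stake is the population in which CD73 and the T-cell subsets are measured. Section 2.7 puts T-cell-mediated inflammation in the study hypothesis, and section 11 puts the inflammation data in the main publication. Appendix 16.7 says that flow samples are discarded after analysis and none is saved. Recorded data could be re-gated without DAPI, but a valid viability reading could not be recovered later.

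**Working it through.** The documents state no rate, sample size or error level for this assay, so there is no figure to reproduce. The check is a reading of section 5.5 against sections 2.6, 5.2 and 9.6 and Appendix 16.7.

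1. **State of the cells.** Section 5.5 has them "following fixation, permeabilized (BD Cytofix/CytopermTM) for intracellular staining". The wording leaves unclear whether the surface stain comes before or after fixation. Either way, the cells described are permeabilised when they are acquired.

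2. **What the gate means.** The plan itself equates DAPI-negative with viable. That equation requires membranes that exclude the dye.

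3. **What the gate covers.** The sentence names three readouts: CD3+ percentage, CD4+/CD8+ subsets and CD73. It does not name IFN-γ or TNF-α, and no gate is stated for them.

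4. **How many preparations.** Section 5.5 describes one. It mentions no separate unfixed tube.

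5. **The panels side by side.** Section 5.2 has CD73 on PE and CD8 on APC, and lists DAPI. Section 5.5 has CD73 on PeCy7 and CD8 on PerCP, and does not list DAPI. The change leaves PE and APC free, which would fit cytokine antibodies added to the same tube. That is an inference, since the cytokine conjugates are not given. The missing DAPI fits either a gate carried over from section 5.2 or a separate surface stain.

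6. **The two possible readings.**
   - *One tube, DAPI read on permeabilised cells.* By steps 1 and 2 the gate does not identify viable cells. The CD73 and subset values, and the myeloid values obtained the same way, rest on an invalid gate.
   - *Two tubes, surface markers and DAPI on an unfixed aliquot, cytokines on a fixed one.* The CD73 and subset values are sound. The cytokine-stained cells have no stated viability gate, and CD73 from the unfixed tube can be related to IFN-γ per patient but not per cell.

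7. **Which reading the text supports.** Steps 1 and 4 favour one tube. Nothing excludes two. Section 2.6 does not say whether the correlation is per cell or per patient, and section 9.6 names only group comparisons, so neither settles it.

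**The case against.** The strongest reply is that section 5.5 is an unclear methods paragraph rather than a faulty assay. No sentence says that DAPI is added after permeabilisation. Every readout named with the gate can be measured without permeabilising the cells. DAPI appears in the unfixed panel of section 5.2 and not in that of section 5.5, and Appendix 16.7 describes surface staining and cytometry with no fixation. The laboratory may already run a separate unfixed tube, and the order of reagents is a detail that some protocols leave to a laboratory manual.

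Part of this stands: the defect is conditional on the one-tube reading. It does not clear the text, because the two-tube reading is nowhere described, leaves the cytokines without a viability gate and restricts the correlation to patient level.

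Three stronger inferences are tempting, and the documents do not support them:

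- *That the cytokines are themselves measured in DAPI-negative cells*, and so in cells selected for weak cytokine staining. The gate sentence does not name them.
- *That this is the only randomised in-vivo measure of inflammation.* Section 5.1 has white-cell sub-populations measured by flow cytometry, with blood drawn at four times, and section 5.3 (adenosine production) is not limited to samples taken before study drug.
- *That the number of cells left in the gate can be calculated.* Section 9.6 gives expected cell yields, but any count of DAPI-negative cells would depend on a permeabilisation efficiency that the documents do not give.

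**Conclusion.** The point holds in conditional form. As section 5.5 most naturally reads, its viability gate is applied to permeabilised cells and does not select viable ones. The gate that defines the CD73 and subset side of the CD73/IFN-γ correlation is then invalid, and so is the corresponding myeloid gate. If an unfixed second tube is intended, those measures stand, but section 5.5 needs to say so and to state a gate for the cytokines.

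The conclusion assumes that DAPI is read after permeabilisation and that DAPI marks dead cells by membrane exclusion. The second is general laboratory knowledge, not stated in the documents, although the plan's own equation of DAPI-negative with viable depends on it.

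No numerical size can be given. CD73 and the cytokines are not among the primary, secondary efficacy or safety outcomes in section 3.11, so the early-onset pneumonia comparison, its sample size and the safety analysis are unaffected. The change is worth making because it is cheap and because these data are meant for the main publication.

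**What to change.** In section 5.5, replace the DAPI gate with a fixable (amine-reactive) viability dye applied before fixation. Gate on cells negative for that dye for surface markers and cytokines alike, in lymphocytes and myeloid cells. This keeps CD73 and IFN-γ paired in the same cell. State the order of surface stain, viability dye, fixation, permeabilisation and intracellular stain, and list the dye in the panel.

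If an unfixed, DAPI-gated aliquot is used for the surface markers instead, describe both tubes, state how the cytokine-stained cells are gated, and limit the CD73/IFN-γ correlation to the patient level.

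If samples have already been run, record the tubes and gate actually used before any CD73 or cytokine result is reported.

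The dye route costs one reagent, one detector channel and a few lines of text. It needs no extra blood or visit. The two-tube route needs no new dye but gives up the per-cell pairing.

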6.1. Baseline Data

- Hospital
- Age (years)
- Sex (male or female as assigned at birth or in the medical record)
 - Gender cannot be reliably collected because all patients are comatose
- Height (centimeters)
- Weight (kilograms)
- Body mass index (kg/m²)
- Race
- Ethnicity
- Smoking Status
- Living environment prior to cardiac arrest
- Pre-arrest diseases
- Charlson Comorbidity Index (total)
- Modified Rankin Score
- Cerebral Performance Category (CPC) prior to cardiac arrest
- Immunosuppressive drugs prior to admission
 - o Cyclosporine
 - Tacrolimus
 - \circ Sirolimus
 - o Everolimus
 - \circ Mycophenolate
 - Enteric-coated mycophenolic acid
 - o Mizoribine
 - o Leflunomide
 - Azathioprine
 - Horse or rabbit antithymocyte globulin
 - o Muromonab-CD3
 - o Alemtuzumab
 - o Rituximab
 - o Basiliximab

- Belatacept
- o Eculizumab
- o Bortezomib
- Methotrexate
- Cyclophosphamide
- Chlorambucil
- o Tofacitinib
- o Abatacept
- o Adalimumab
- o Anakinra
- Certolizumab
- o Etanercept
- o Golimumab
- o Infliximab
- o Ixekizumab
- o Natalizumab

- o Rituximab
- o Secukinumab
- Tocilizumab
- o Ustekinumab
- Vedolizumab
- Daclizumab
- o Hydroxychloroquine
- o Sulfasalazine
- o Dapsone
- Rilonacept
- Sarilumab
- o Eculizumab
- o Belimumab
- o Brodalumab

6.3. ICU Admission Data

- ICU Admission Date and Time
- Sequential Organ Failure Assessment worst (highest) score within 24 hours of admission
- Acute Physiology and Chronic Health Evaluation IV score within 24 hours of hospitalization
 - o The APACHE IV score will be retrospectively calculated on all enrolled PROTECT subjects
- Acute Physiology Score
- Predicted LOS
- Glasgow Coma Scale score
- Targeted Temperature Management (yes, no, or unknown)
- Time from ROSC to target temperature
- Duration of TTM
- Target temperature
- STEMI (yes, no, or unknown)
- Cardiac angiography intervention (yes, no, or unknown)
- Shock on admission (SBP <90 mmHg for 30 minutes or need for vasoactive medications/ mechanical circulatory support)

6.4. ICU Discharge Data

- Early-onset pneumonia (yes or no)
 - Clinical (yes or no; list criteria for diagnosis)
 - Microbiologically-confirmed (yes or no; list organism and criteria for diagnosis)
- Late-onset pneumonia (yes or no)
 - Clinical (yes or no; list criteria for diagnosis)
 - Microbiologically-confirmed (yes or no; list organism and criteria for diagnosis)
- Non-pulmonary infection (yes or no)
 - List infection and organism, when available
- ICU-free days in the first 28 days of admission (days)
- Mechanical Ventilation duration (days)
- Mechanical ventilator-free days in the first 28 days of admission (days)
- Rearrest in the ICU requiring CPR
- ICU LOS (days)
- ICU mortality (yes or no)
- Date and time of first dose of study drug
- Date and time of last dose of study drug
- Total doses of study drug administered
- Total missed doses of study drug
- Date and times of missed study drug doses
- Study drug discontinuation
- Reasons for study drug discontinuation

• Days of antibiotic spectrum coverage

6.5. Hospital Discharge Data

- mRS score (0-6)
- CPC score (1-5)
- Hospital LOS (days)
- Discharge disposition (select)
 - o Home
 - o Inpatient Rehabilitation
 - o Inpatient ventilator unit
 - Skilled Nursing
 - Hospice facility
 - Death (list cause of death including withdrawal of life support)
- Date and time of death
- Cause of death (free text field in addition to information collected above in TTM database)
- Location of patient death
 - o ICU
 - o Hospital
- Date and time of discharge

6.6. Six Month Data (After cardiac arrest)

- mRS score (0-6)
- CPC score (1-5)
- Did patient die post-discharge?
- Date and time of death
- Cause of death

7. Data Management

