2.2. Pneumonia after Cardiac Arrest

Pneumonia is an infection of the lungs resulting in alveolar inflammation and fluid or purulent material accumulation. It is the most common infection after cardiac arrest occurring in up to 65% of patients treated with TTM.⁶ Infections are associated with increased intensive care unit (ICU) length of stay (LOS), hospital LOS, duration of mechanical ventilation, post-discharge rehabilitation need, tracheostomy, and mortality, while also reducing the incidence of a good functional outcome.⁷⁻¹¹

Pneumonia results from aspiration during cardiopulmonary resuscitation (CPR), or by introduction of oropharyngeal flora into the lungs during airway management. It may also be due to gastrointestinal hypoperfusion, which leads to ischemic injury to the intestinal mucosa, bacterial translocation, and hematogenous spread. Infection might also be the result of post-resuscitation immune suppression.¹²⁻¹⁸ The association between infection and morbidity and mortality justifies further study.

Preventing infection after OHCA may: 1) reduce exposure to broad-spectrum antibiotics and subsequent collateral damage, 2) prevent hemodynamic derangements due to local and systemic inflammation, and 3) prevent an association between infection and morbidity and mortality. These benefits must be balanced with the risk for altering bacterial resistomes in the absence of clinical infection. Accordingly, further study is warranted to understand the risk-to-benefit ratio of prophylactic antibiotics.

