3.15. Follow-up

Patients will be followed for the duration of their hospitalization and up to six months after cardiac arrest. At the time of hospital discharge, a research coordinator will determine each patient's mRS score and CPC. This will also occur at six months after cardiac arrest via telephone call.

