9.4. Safety Outcomes

The safety endpoints will be analyzed on an intention-to-treat basis. Safety outcomes will be reported as proportions and study groups compared using the Chi-square test or Fisher exact test, as appropriate.

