10.2. Pneumonia Adjudication Board

A pneumonia adjudication board will be assembled prior to the trial's commencement. It will adjudicate all clinically diagnosed and microbiologically confirmed pneumonia. Their work will be done in a blinded fashion. Disputes will be reconciled through communication or with the assistance of a third adjudicator. Members of the pneumonia adjudication board will include:

- a. Xxxx
- b. Xxxx
- c. Xxxx
- d. (2018)

11. Publication

Analyses will be performed six months after cardiac arrest of the last patient. Data analysis will be performed in a blinded manner. The full-length manuscript will be submitted to a peer-reviewed international medical journal. Authorship will follow the guidelines set forth by the International Committee of Medical Journal Editors. The main publication will include the primary and secondary efficacy outcomes, safety outcomes, inflammation data, and resistome data. Subsequent publications may be considered by the study investigators at the conclusion of the trial.

12. Funding

The trial will be funded by xxxx as part of a xxxx grant for acute care research and rural disparities. The funding source has approved the scientific merit of the trial, but will not be involved with its conduct, data analysis, manuscript development, or decision to submit for publication.

13. Timeline/Sequence of Events

1/2021 to 5/2021 – trial design, EFIC process, IRB approval

5/2021 to 6/2022 - recruitment of 60 patients, follow-up data collection, interim analysis

6/2022 to 2/2023 – recruitment of remaining 60 patients, follow-up data collection

2/2023 to 8/2023 – data analysis, preliminary data, presentation of preliminary results

8/2023 - final follow-up data collected, full data analysis, submission for publication

Sequence of Events

	By 6 hours of ICU admissi on	0-24 hours after administrati on of first dose of study drug	24-48 hours after administrati on of first dose of study drug	48-72 hours after administrati on of first dose of study drug	72-96 hours after administrati on of first dose of study drug	96-120 after administrati on of first dose of study drug	144-168 hours after administrati on of first dose of study drug	Day 1 to hospital dischar ge	Hospita I dischar ge	Six- mont h follo w-up
Screening/enrollm ent	x									
Study drug	х	Х	Х	Х						
Sputum sample	X*◊				X◊					
Rectal swab	X*◊				X◊		X ^{◊Δ}			
Blood sample	X*◊	X◊		X◊		X◊				
EOP		Х	Х	Х						
Non-pulm. infection								x		

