ICU LOS								х		
Ventilator-free days								х		
Hospital LOS								х		
ICU mortality								х		
Hospital mortality								х		
Discharge disposition								x		
CDAD								х		
Type-one allergy		Х	Х	Х						
Gallbladder disease								x		

mRS					х	Х
CPC					Х	Х

CDAD = *Clostridioides difficile*-associated diarrhea; EOP = early-onset pneumonia; ICU = intensive care unit; LOS = length of stay; mRS = modified Rankin Scale; CPC = Cerebral Performance Category; The initiation of the study drug=time zero hours

*Blood, Sputum sample, and Rectal swab must be obtained after informed consent and prior to administration of first dose of study drug

^b Missing time points does not disqualify patient for study participation and is not a protocol deviation.

^A If discharge occurs before 144-168 hrs after administration of first dose of study drug, collect this rectal swab on day of discharge

14. Trial Participants

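### C. difficile and gallbladder events are sought only until hospital discharge, a point that treatment may shift, so cases can be missed and the crude comparison may be biased in either direction

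*Combined protocol and SAP*

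**What the plan says.** The Sequence of Events table in Section 13 has a CDAD row and a "Gallbladder disease" row. Each is marked in one column only, the one running from day 1 to hospital discharge, and neither is marked at six months. The third safety outcome, type one hypersensitivity, is marked over the first 72 hours after first dose, so its window is the same in both arms.

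Section 3.11.3 defines the two events (a positive toxin-gene PCR with new diarrhea; a sonographic finding) but gives no counting period.

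Section 3.15 states: "Patients will be followed for the duration of their hospitalization and up to six months after cardiac arrest". The assessments it names at discharge and six months are mRS and CPC. Section 6.6 adds "Did patient die post-discharge", with date and cause of death.

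The introduction to Section 6 says that "information on serious adverse events, study drug and trial completion will be collected", without an end date. Section 8.4 lists both events as study-specific serious adverse events.

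Section 9.4 gives the analysis: "Safety outcomes will be reported as proportions and study groups compared using the Chi-square test or Fisher exact test, as appropriate".

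Hospital length of stay is a secondary efficacy outcome (Section 3.11.2). Section 2.2 says: "Infections are associated with increased intensive care unit (ICU) length of stay (LOS), hospital LOS, duration of mechanical ventilation". It also links infection to mortality. Section 8.1 expects 40-50% of these patients to die in hospital.

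**The concern.** A safety count is easiest to interpret when both arms are watched for the same planned time. Here the count stops at discharge, which comes after randomization and which the trial also tests as a treatment effect. If ceftriaxone changes how long patients stay, or how many die in hospital, it also changes how long they are watched. Section 9.4 treats the two arms as if they were observed equally.

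A second loss does not depend on any difference between arms: an event that arises after discharge is not looked for, although a telephone call at six months is already planned.

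CDAD and gallbladder disease are two of only three listed safety outcomes, and both are named in the harm rule of Section 8.3. Few events can be expected in 120 patients, so each missed case matters.

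**Working it through.** **1. The plan's own figure.** Section 9.1 gives 60 per arm for 80% power, EOP 55% versus 30%, two-sided 5%. With pooled variance under the null:

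n = [1.96 × √(2 × 0.425 × 0.575) + 0.842 × √(0.55 × 0.45 + 0.30 × 0.70)]² / 0.25² ≈ 60.2, that is 61 per arm.

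Power at 60 per arm is 79.9%, so the figure reproduces. The documents give no figure for the safety outcomes, length of stay or time at risk. Every stay length below is an assumption.

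**2. How short the window can be.** A footnote to the Section 13 table foresees early discharge: "If discharge occurs before 144-168 hrs after administration of first dose of study drug, collect this rectal swab on day of discharge". Dosing every 12 hours for three days is six doses, at 0, 12, 24, 36, 48 and 60 h. Discharge at 144 h leaves 144 − 60 = 84 h (3.5 days) after the last dose. Discharge at 168 h leaves 108 h (4.5 days).

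**3. Mean observation time per arm.** Let S be the stay of survivors, D the stay of patients who die in hospital, and m in-hospital mortality:

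T = (1 − m) × S + m × D

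- From the documents: m = 45% (midpoint of 40-50%, Section 8.1) and a 25-point EOP reduction (Section 9.1).
- Assumed: S = 14-25 days, D = 4-7 days, and 3-7 extra days per pneumonia in survivors. On ceftriaxone, S falls by 0.25 × extra days.

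No mortality effect:
- Largest reduction (S = 14, D = 4, 7 extra days): control 0.55 × 14 + 0.45 × 4 = 9.50; ceftriaxone 0.55 × 12.25 + 0.45 × 4 = 8.54; ratio 0.90.
- Smallest reduction (S = 25, D = 7, 3 extra days): control 16.90; ceftriaxone 0.55 × 24.25 + 0.45 × 7 = 16.49; ratio 0.98.

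Mortality also 10 points lower on ceftriaxone (45% to 35%):
- Lowest ratio (S = 14, D = 7, 7 extra days): (0.65 × 12.25 + 0.35 × 7) / 10.85 = 0.96.
- Highest ratio (S = 25, D = 4, 3 extra days): (0.65 × 24.25 + 0.35 × 4) / 15.55 = 1.10.

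The mortality reduction at which the two effects cancel is x = (1 − m) × 0.25 × extra days / (S on ceftriaxone − D). Over the assumed ranges it runs from 0.4125 / 20.25 = 2 points to 0.9625 / 5.25 = 18 points.

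**4. Effect on the risk ratio.** Assume a 3% control risk and a constant hazard h = −ln(0.97). With f the ratio of observation times, the observed risk ratio is [1 − exp(−h × HR × f)] / 0.03.

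| True hazard ratio | f = 0.90 | f = 1.00 | f = 1.10 |
|---|---|---|---|
| 1 | 0.90 | 1.00 | 1.10 |
| 1.5 | 1.34 | 1.49 | 1.63 |
| 2 | 1.78 | 1.97 | 2.16 |

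**5. Could the difference in stay be much larger?** Let b be the mean stay without pneumonia and d the extra stay per pneumonia, in all patients. The arm means are b + 0.55d and b + 0.30d. A mean stay 30% shorter on ceftriaxone requires b + 0.30d = 0.70 × (b + 0.55d), so 0.30b = 0.085d and d = 3.53b. Pneumonia would have to make the stay about 4.5 times as long. A 10% shorter stay requires 0.10b = 0.195d, so d = 0.51b.

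**6. Power for these events.** Exact Fisher power at 60 per arm is 3.3% for 3% versus 6%, and 13.8% for 3% versus 9%. At the interim look (30 per arm) it is 0.3% and 2.1%. The risks are assumed.

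**The case against.** The strongest reply has four parts.

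- **Direction.** A reader might infer that ceftriaxone patients are watched for less time, so the comparison leans toward no harm. The documents do not say this. Section 2.2 reports associations only, without a number of days, and links infection to mortality as well as to stay. Death also closes the window, so a survival benefit could lengthen observation on ceftriaxone. This objection stands.
- **Size.** A reader might also suppose that a much shorter stay could nearly erase a true excess. Step 5 shows how long a pneumonia stay that would require. The early-discharge footnote is a contingency for one rectal swab, applies to both arms, and does not say how often early discharge occurs. This stands too.
- **Other routes to detection.** It would be too strong to say that later cases can never be found. Both events are study-specific serious adverse events, serious adverse event collection has no stated end, and hospitalization is itself a seriousness criterion in Section 8.1. A late report is therefore possible. But no procedure seeks one, so the gap in active ascertainment remains.
- **Practical effect.** With the power in step 6, a few percent of observation time will rarely change a conclusion. That limits the importance of the bias. It does not justify leaving events uncounted when they are already few.

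Section 2.5 notes that controls may receive longer broad-spectrum courses. Any effect of that on C. difficile is a real consequence of the treatment strategy, not an observation-time bias.

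**Conclusion.** The point holds in a limited form. Scheduled ascertainment of CDAD and gallbladder disease ends at an outcome-dependent time, the six-month contact does not ask about either, and Section 9.4 makes no allowance for unequal observation. Cases may be missed and the comparison may be biased.

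The sign is unknown. The ratio of mean observation time (ceftriaxone to control) is about 0.90-0.98 if stay shortens with no mortality effect, and about 0.96-1.10 if mortality also falls by 10 points. These ranges rest on assumed stays, a constant event rate and 45% in-hospital mortality. The bias concerns only events that would arise after discharge. It is probably modest, and low power is the larger limit on what the trial can say about these harms. The change is still worth making, because it is cheap and improves the safety count whichever way the bias runs.

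**What to change.** - **Section 13 schedule and Section 3.11.3:** count both events over the same fixed window from first dose in both arms, for example to day 28, the length of horizon Section 3.11.2 already uses for ICU-free and ventilator-free days. Take post-discharge events from the hospital record and confirm them against the Section 3.11.3 definitions. Record the date of each event.
- **Section 6.6:** add one question for each event to the six-month call. Recall cannot satisfy the PCR or sonographic criteria, so report recall-only events separately as unconfirmed and keep them out of the main count.
- **Section 9.4:** use the fixed-window proportion, with a sensitivity analysis treating death as a competing event. A fixed window makes the planned periods equal, but death will still cut observation short in many patients. The death and discharge dates needed are already collected (Sections 6.5 and 6.6).

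The cost is a day-28 record check, a few data fields and two questions on a call already planned. The remaining weakness is incomplete capture of patients discharged to other facilities, and the call reaches survivors only. Both limits should be stated with the results.
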